#### 3.4 SAFETY MEASUREMENTS

# 3.4.1 Clinical and Laboratory Measurements for Safety

All patients who receive one or more doses of study therapy will be evaluated for the presence of adverse experiences while on study therapy and through the 2-week posttherapy follow-up visit. To assist with these safety assessments, a physical examination will be performed at prestudy, twice weekly throughout the study therapy period (including Day 4 and Day 7), on the last day of study therapy, and at the 2- and 8-week posttherapy follow-up visits. In addition, selected laboratory safety tests will be performed at screening, on Day 4 (or Day 3 or Day 5) and Day 7 of study therapy, twice weekly thereafter while on study therapy, on the last day of study therapy, and at the 2-week posttherapy follow-up visit (see Appendix 6.1).

To address the secondary safety objective, the following safety endpoints will be evaluated: (1) the development of adverse experience(s) during the study therapy period or during the 2-week posttherapy follow-up period; (2) the development of drug-related adverse experience(s) during the study therapy period or during the 2-week posttherapy follow-up period; (3) the development of serious adverse experience(s) during study therapy period or during the 2-week posttherapy follow-up period; (4) the development of drug-related, serious adverse experience(s) during study therapy period or during the 2-week posttherapy follow-up period; (5) the development of adverse experiences that necessitate discontinuation of study therapy; and (6) the development of drug-related adverse experiences that necessitate discontinuation of study therapy.

**Protocol/Amendment No.:** 064-02

# 3.4.2 Management of Adverse Events

Patients will be monitored for any evident adverse experiences at all study visits (through the 2-week posttherapy follow-up visit), and the information will be recorded on the appropriate eCRF. Decisions to temporarily withhold study therapy because of an adverse experience will be reviewed on a case-by-case basis by the investigator. Guidelines for managing certain adverse experiences are presented below. The investigator will use discretion in the application of these guidelines.

For those circumstances not described below that require a hold on administration of study therapy, it may be possible to reinitiate study therapy upon resolution of the laboratory abnormality or clinical adverse experience. Individual cases should be discussed with the investigator and SPONSOR Clinical Monitor (or designee).

# Liver Enzyme Abnormalities

Safety assessments of injury or damage to the liver will be performed by monitoring of liver function tests during and at the end of study therapy. Laboratory tests should be repeated if AST or ALT increase to ≥2 times the baseline value. If on repeated measures, the laboratory test elevated at study entry continues to rise (and reaches 6 times the upper limit of normal), study therapy should be discontinued as described in Section 3.2.3.7.1. However, if the enzyme elevations are clearly due to another etiology, the case may be discussed with the SPONSOR Clinical Monitor (or designee) prior to discontinuing the patient from study therapy. If liver enzymes return to normal, rechallenge with the study therapy may be allowed. The decision will be made by the investigator in consultation with the SPONSOR Clinical Monitor (or designee).

Any elevated AST or ALT lab value that is greater than or equal to 3 X the upper limit of normal and an elevated total bilirubin lab value that is greater than or equal to 2 X the upper limit of normal and, at the same time, an alkaline phosphatase lab value that is less than 2 X the upper limit of normal, as determined by way of protocol-specified laboratory testing or unscheduled laboratory testing will be evaluated. The trial site guidance for assessment and follow up of these criteria can be found in the Administrative Binder.

#### Other Adverse Experiences

While receiving study therapy, patients who develop any adverse experience that is felt to possibly be related to the study drug, and for which interruption of therapy is clinically indicated, should have their study therapy stopped.

# 3.4.3 Recording Adverse Experiences

An adverse experience is defined as any unfavorable and unintended change in the structure, function, or chemistry of the body temporally associated with the use of the SPONSOR's product, whether or not considered related to the use of the product. Any worsening (i.e., any clinically significant adverse change in frequency and/or intensity) of a preexisting condition which is temporally associated with the use of the SPONSOR's product, is also an adverse experience.

**Protocol/Amendment No.:** 064-02

Changes resulting from normal growth and development which do not vary significantly in frequency or severity from expected levels are not to be considered adverse experiences. Examples of this may include, but are not limited to, teething, typical crying in infants and children, and onset of menses or menopause occurring at a physiologically appropriate time.

Adverse experiences may occur in the course of the use of a Merck product in clinical studies or within the follow-up period specified by the protocol, or prescribed in clinical practice, from overdose (whether accidental or intentional), from abuse, and from withdrawal.

Adverse experiences may also occur in screened subjects/patients during any preallocation baseline period as a result of a protocol-specified intervention including washout or discontinuation of usual therapy, diet, placebo treatment, or a procedure.

Such events will be recorded at each examination on the Adverse Experience Case Report Forms/Worksheets.

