#### 3.2.3.7.1 Discontinuation/Withdrawal Criteria

Discontinuation from study therapy should be done for the following reason(s):

- The patient's parent (or guardian) refuses further treatment or follow-up and withdraws consent.
- Continuation is not in the best interest of the patient, in the judgment of the investigator.
- Failure to demonstrate or sustain clinical improvement after a course of study therapy. In general, patients who do not have some clinical evidence of improvement by Day 7 of therapy should be discontinued.
- Significant progression of invasive candidiasis after at least 72 hours of study therapy.
- The need to increase the dose of the antifungal study therapy or to give another systemic antifungal drug in addition to the antifungal study therapy.
- Development of signs or symptoms of a rapidly progressive underlying disease that would preclude evaluation of therapy, or that would render continuation in the study inadvisable, in the judgment of the investigator.
- Development of concomitant fungal infection with an organism that is not susceptible to the antifungal study therapy.
- Instances in which pretherapy or follow-up microbiologic studies indicate that the etiologic pathogen(s) of the index infection is/are not susceptible to amphotericin B deoxycholate and/or caspofungin.
- Development of a serious adverse experience related to study therapy or the occurrence of an adverse clinical experience or clinically significant laboratory change or abnormality that, in the judgment of the investigator, warrants withdrawal of the patient from the antifungal study therapy.
- An elevated AST or ALT lab value that is greater than or equal to 3 X the upper limit of normal and an elevated total bilirubin lab value that is greater than or equal to 2 X the upper limit of normal and, at the same time, an alkaline phosphatase lab value that is less than 2 X the upper limit of normal, as determined by way of protocol-specified laboratory testing or unscheduled laboratory testing. NOTE: Patients will be discontinued from study therapy but followed for safety until the abnormal value(s) has/have normalized, stabilized, or returned to baseline.
- Development of nephrotoxicity, which in the opinion of the investigator, warrants discontinuation of study therapy.

**Protocol/Amendment No.:** 064-02

• Requirement for treatment with an investigational drug.

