# 3.4.5 Immediate Reporting of Adverse Experiences to the SPONSOR

# 3.4.5.1 Serious Adverse Experiences

Any serious adverse experience, including death due to any cause, which occurs to any subject/patient entered into this study or within 14 days following cessation of treatment or within the established off therapy follow-up period for safety described in the protocol,

**Protocol/Amendment No.:** 064-02

whether or not related to the investigational product, must be reported within 24 hours to one of the individual(s) listed on the contact information page.

Additionally, any serious adverse experience considered by an investigator who is a qualified physician to be possibly, probably, or definitely related to the investigational product that is brought to the attention of the investigator at any time outside of the time period specified in the previous paragraph also must be reported immediately to one of the individuals listed on the sponsor contact information page found in the administrative binder.

All subjects/patients with serious adverse experiences must be followed up for outcome.

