P-values (Tier 1 only) and 95% confidence intervals (Tier 1 and Tier 2) will be provided for between-treatment differences in the percentage of patients with events; these analyses will be performed using the Miettinen and Nurminen method (1985), an unconditional, asymptotic method. For this protocol, there are no Tier 1 events.

**Protocol/Amendment No.:** 064-02

Table 3-7
Analysis Strategy for Safety Parameters

Safety Tier	Safety Endpoint a	p-Value	95% CI for Treatment Comparison	Descriptive Statistics
Tier 1	None			
Tier 2	Any AE Any Serious AE Any Drug-Related AE Any Serious and Drug-Related AE Discontinuation due to AE Discontinuation due to a Drug-Related AE Specific AEs, SOCs, or PDLCs b (incidence ≥4 in one of the treatment groups)		X X X X X X	X X X X X X
Tier 3	Specific AEs, SOCs or PDLCs b (incidence <4 in all of the treatment groups) Change from Baseline Results (Labs, ECGs, Vital Signs)			X X

<sup>a Adverse Experience references refer to both Clinical and Laboratory AEs.

Note: SOC=System Organ Class; PDLC=Pre-Defined Limit of Change; X = results will be provided.

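### The all-cause serious-AE and AE-discontinuation comparisons mix Candida treatment failure with toxicity, and no planned all-cause summary leaves index-infection events out

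*Combined protocol and SAP*

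**What the plan says.** Section 3.4.3 defines an AE without regard to cause ("whether or not considered related to the use of the product") and extends it to any "worsening (i.e., any clinically significant adverse change in frequency and/or intensity) of a preexisting condition which is temporally associated" with the product. It has one exemption: "Changes resulting from normal growth and development which do not vary significantly in frequency or severity from expected levels are not to be considered" AEs. Neither the protocol nor the SAP exempts the infection under treatment.

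Section 3.4.5.1 requires expedited reporting of "Any serious adverse experience, including death due to any cause, which occurs to any subject/patient entered into this study", and Table 3-5 lists death among the criteria for a serious AE.

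Section 3.2.3.7.1 lists reasons for stopping study therapy. Lack of improvement and "Significant progression of invasive candidiasis after at least 72 hours of study therapy" are separate entries from the one for AEs. Table 3-5 then asks of each AE whether it led to the test drug being stopped.

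The safety endpoints in 3.4.1 and 3.5.4.2 include any AE, serious AEs and "the development of adverse experiences that necessitate discontinuation of study therapy", each with a drug-related counterpart. The window for the first two and their counterparts closes at the 2-week posttherapy visit, which is also the primary efficacy time point. In Table 3-7 all six are Tier 2, including the row "Discontinuation due to AE", so each gets a between-arm 95% CI. There are no Tier 1 events.

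**The concern.** All enrolled infants have culture-confirmed candidiasis at entry, so the worsening clause applies to the index infection in every one of them. Progression, relapse or fatal candidiasis can count both as failure of fungal-free survival and as an AE, often a serious one, over largely the same period.

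The trial is designed around a 30-point efficacy difference. To the extent that failures are recorded as AEs, part of that difference passes into the all-cause safety rows. A more effective drug then looks safer, and a less effective one more toxic, with no difference in toxicity.

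The discontinuation row has a further ambiguity. A stop for progression meets its own criterion in 3.2.3.7.1, and the same event is an AE that led to stopping. The protocol does not say whether such a stop enters the AE-discontinuation row, so sites could record it differently.

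**Working it through.** **1. Which rows are exposed**

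- *Any Serious AE*: the firmest case. Death from any cause is reportable as a serious AE and is also a failure of the primary endpoint, so the two share events whatever the coding of progression.
- *Discontinuation due to AE*: exposed to the extent that progression stops are also recorded as AEs that caused discontinuation.
- *Any AE*: exposed in principle, but an infant who already has another AE cannot be counted twice, so a high background rate absorbs most of the effect.

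**2. Inputs**

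- From the SAP: 60 and 30 patients; response of 80% and 50% (3.5.8.1, Table 3-8), hence failure of 20% and 50%; Miettinen-Nurminen 95% intervals (3.5.6.2); 23.7% as one background value (3.5.8.2, a drug-related AE rate in older children).
- Assumed: toxicity rate *t* equal in both arms and independent of failure; background values of 10% and 80%; share *f* of failures recorded as AEs, from 0 to 100%. The documents do not give *f*.

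**3. The plan's own figures**

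Sample size for 80% vs 50%, 2:1, 80% power, two-sided 5%, pooled variance, no continuity correction. The pooled rate is (2 × 0.80 + 0.50)/3 = 0.70.

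n(amphotericin) = [1.96 × √(1.5 × 0.70 × 0.30) + 0.8416 × √(0.50 × 0.50 + 0.80 × 0.20/2)]² / 0.30² = (1.100 + 0.483)² / 0.09 ≈ 27.9, so 28.

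That gives 56:28 = 84, as in Table 3-8. Seven cells of Table 3-9, recomputed with the N/(N−1) variance factor, agree to within 0.1 point.

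**4. Model for an all-cause safety row**

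Rate in an arm = 1 − (1 − t)(1 − f × failure rate).

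Difference (caspofungin minus amphotericin B) = −(1 − t) × f × (0.50 − 0.20).

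Example, t = 10%, f = 50%: caspofungin 1 − 0.90 × 0.90 = 19.0%; amphotericin B 1 − 0.90 × 0.75 = 32.5%; difference −13.5 points.

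**5. How often the interval would point to a safety difference**

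The table gives the chance that the 95% CI excludes zero in favour of caspofungin at 60:30, by exact enumeration of both binomials. True toxicity is equal throughout.

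| Background t | f = 0 | f = 25% | f = 50% | f = 100% | Shift at f = 100% |
|---|---|---|---|---|---|
| 10% | 2.8% | 14.1% | 30.5% | 70.8% | −27.0 points |
| 23.7% | 2.8% | 8.4% | 19.1% | 52.5% | −22.9 points |
| 80% | 2.2% | 3.2% | 4.5% | 9.7% | −6.0 points |

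**6. Single intervals at expected counts, half of failures recorded**

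- t = 10%: 11/60 vs 10/30, difference −15.0 (−35.1, 3.4).
- t = 23.7%: 19/60 vs 13/30, difference −11.7 (−32.6, 9.0).

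Both include zero. The effect is a raised chance of an apparent difference, not a certain one.

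**The case against.** The strongest reply is that the plan already separates the two sources to a fair degree. Table 3-7 has a drug-related version of each summary row. It also has rows for specific AEs and system organ classes, with a 95% CI once four patients in one arm have the event and counts below that. Efficacy is reported in its own table. Section 3.5.6.2 calls the safety intervals descriptive, and with no Tier 1 events no formal conclusion rests on them. All of this stands. What it does not supply is an all-cause total without index-infection events. The drug-related rows depend on investigator attribution, and specific-event rows do not add up to a patient-level summary.

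Three stronger readings are tempting and should be resisted.

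- *The whole 30-point difference flows into safety.* Failures through missing data (3.5.6.1), further antifungal treatment after therapy (3.5.4.1.2) or persistence without worsening are not worsenings. Recording all failures is a ceiling.
- *Half the failures would be enough to exclude zero.* Infection events alone, 6/60 vs 8/30, give −16.7 (−35.7, −0.7). That assumes no toxicity at all and rounds 7.5 up to 8; 6/60 vs 7/30 gives −13.3 (−32.2, 2.0). With 10% background the interval includes zero.
- *Progression stops should be removed from the AE-discontinuation row.* Section 3.2.3.7.1 does not make the two reasons exclusive, so removal would drop patients who meet both.

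It can also be said that divergent coding between sites is conjecture. The eCRF and data-management procedures lie outside these documents (3.7) and may contain a rule. That is fair: the gap shown is in the protocol and SAP only.

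**Conclusion.** The point holds in a limited form. On the text, index-infection worsening and death count as AEs, so Any Serious AE and Discontinuation due to AE in Table 3-7 mix treatment failure with toxicity, and no planned all-cause summary excludes those events. The clause does not name Candida; inclusion follows from its general wording and the single exemption.

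The size depends on the background rate and on the share of failures recorded as AEs, which is unknown. With low background and a quarter to a half of failures recorded, an interval favouring caspofungin becomes roughly five to eleven times as likely as with none recorded (14.1/2.8 and 30.5/2.8). With background near 80% the effect is small. These results also rest on equal, independent toxicity and on the design response rates being true.

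A reader might infer that the report could not tell toxicity from failure, or that the trial's inference is compromised. The documents support neither: partial separation is planned, the safety intervals are descriptive, and the primary test and sample size are untouched. The change is worth making because these intervals are the only between-arm safety comparison the trial offers.

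**What to change.** Keep all current rows and all reporting duties, and add:

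1. An eCRF flag, set while blinded, for AEs that are worsening or relapse of, or death from, the index Candida infection.
2. Supplementary rows in Table 3-7 for Any Serious AE, Discontinuation due to AE and Any AE excluding flagged events, beside the existing rows, with deaths in a row of their own.
3. One recorded primary reason for each stop under 3.2.3.7.1, collected the same way at every site, so that stops for lack of improvement or progression can be shown separately from other AE discontinuations. This is a sensitivity display; the existing all-cause row is unchanged.

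The cost is one eCRF item, a primary-reason field if none exists, a short SAP paragraph and a few table rows. The downside is one more blinded investigator judgement, whether an event belongs to the index infection. The flag has to be in place before unblinding, since it could not be assigned cleanly afterwards.

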## 3.4.4 Definition of an Overdose for This Protocol

Any overdose, whether or not associated with an adverse experience, must be reported within 24 hours to the SPONSOR (or its designee).

For this protocol, an overdose is defined as any daily dose that exceeds 2 times the prescribed dose in a 12-hour period.

# 3.4.4.1 Reporting of Overdose to SPONSOR

If an adverse experience(s) is associated with ("results from") the overdose of test drug or vaccine, the adverse experience(s) is reported as a serious adverse experience, even if no other criteria for serious are met.

If a dose of test drug or vaccine meeting the protocol definition of overdose is taken without any associated clinical symptoms or abnormal laboratory results, the overdose is reported as a non-serious Event of Clinical Interest (ECI), using the terminology "accidental or intentional overdose without adverse effect."

All reports of overdose with and without an adverse experience must be reported within 24 hours to one of the individuals listed on the sponsor contact information page found in the Administrative Binder.

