#### 1.6 DOSAGE/DOSAGE FORM, ROUTE, AND DOSE REGIMEN

Caspofungin will be administered at 2 mg/kg once daily (with no loading dose).

Amphotericin B deoxycholate will be administered at 1 mg/kg once daily.

Initial dosing with the study medications will be based on the patient's actual body weight (in kg) at the time of study entry. The patient is to be weighed at least weekly during the treatment period. The study medication dose (mg) should be adjusted as the patient's weight increases to maintain the mg/kg dose of the assigned treatment throughout the study treatment period.

Caspofungin and amphotericin B deoxycholate will both be administered intravenously over approximately 2 hours. As these 2 products differ in color, opaque masking will be used over the infusion materials (e.g., infusion syringe and tubing) to ensure adequate blinding of the treatment group.

The duration of study therapy with caspofungin or amphotericin B deoxycholate is variable and dependent on a variety of factors, including (1) the rapidity of a patient's clinical and microbiological response, (2) the patient's general medical condition, and (3)

**Protocol/Amendment No.:** 064-02

the underlying site of *Candida* infection. In general, patients should be treated with study therapy for a minimum of 14 days following the time of documented negative cultures from the site of infection and improvement of any clinical signs and symptoms of invasive candidiasis. Certain sites of infection, including *Candida* endocarditis, meningitis, osteomyelitis/septic arthritis, and endophthalmitis, may warrant a longer treatment course based on the consideration of a variety of relevant factors (see Table 2-1 in Section 2.4.2, Treatment Plan).

**Protocol/Amendment No.:** 064-02

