# 3.4.6 Evaluating Adverse Experiences

Refer to Table 3-5 for instructions in evaluating adverse experiences.

**Protocol/Amendment No.:** 064-02

Table 3-5

An investigator who is a qualified physician, will evaluate all adverse experiences as to:

Maximum	Mild	awareness of sign or symptom, but easily tolerated (for pediatric studies, awareness of symptom, but easily tolerated)				
Intensity	Moderate	discomfort enough to cause interference with usual activity (for pediatric studies, definitely acting like something is wrong)				
-	Severe	incapacitating with inability to work or do usual activity (for pediatric studies, extremely distressed or unable to do usual activities)				
Seriousness	A serious adverse experience is any adverse experience occurring at any dose that:					
	†Results in death; or					
	†Is life threatening	; or places the subject/patient, in the view of the investigator, at immediate risk of death from the experience as it occurred [Note: This does not include an adverse				
	experience that, had	lit occurred in a more severe form, might have caused death.]; or				
	†Results in a persi	stent or significant disability/incapacity (substantial disruption of one's ability to conduct normal life functions); or				
		ongs an existing inpatient hospitalization (hospitalization is defined as an inpatient admission, regardless of length of stay, even if the hospitalization is a				
		ure for continued observation). (Note: Hospitalization [including hospitalization for an elective procedure] for a preexisting condition which has not worsened does				
		ous adverse experience.); or				
	†Is a congenital an	omaly/birth defect (in offspring of subject/patient taking the product regardless of time to diagnosis); or				
	Is a cancer; or					
	Is an overdose (Whether accidental or intentional.) Any overdose whether or not associated with an adverse experience must be reported within 24 hours.					
	Other important medical events that may not result in death, not be life threatening, or not require hospitalization may be considered a serious adverse experience when, based upon					
	appropriate medical judgment, the event may jeopardize the subject/patient and may require medical or surgical intervention to prevent one of the outcomes listed previously (designated					
	above by a †).					
Duration	Record the start and stop dates of the adverse experience. If less than 1 day, indicate the appropriate length of time and units					

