Yes, there is a reasof drug relationsh	Definitely related  Probably related  Possibly related  reasonable	There is evidence of exposure to the test drug. The temporal sequence of the AE onset relative to the administration of the test drug is reasonable. The AE is more likely explained by the test drug than by another cause.  Depending on data collection method employed, drug relationship may be further graded as follows:  There is evidence of exposure to the test drug. The temporal sequence of the AE onset relative to administration of the test drug is reasonable. The AE is more likely explained by the test drug than by another cause. Dechallenge is positive. Rechallenge (if feasible) is positive. The AE shows a pattern consistent with previous knowledge of the test drug or test drug class.  There is evidence of exposure to the test drug. The temporal sequence of the AE onset relative to administration of the test drug is reasonable. The AE is more likely explained by the test drug than by another cause. Dechallenge (if performed) is positive.  There is evidence of exposure to the test drug. The temporal sequence of the AE onset relative to administration of the test drug is reasonable. The AE could have been due to another equally likely cause. Dechallenge (if performed) is positive.  Subject did not receive the test drug OR temporal sequence of the AE onset relative to administration of the test drug is not reasonable OR there is another obvious cause of the AE. (Also entered for a subject with overdose without an associated AE.)			

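### An overdose without any associated effect is non-serious in section 3.4.4.1 but meets a seriousness criterion in Table 3-5, and the 12-hour window in the overdose definition does not fit once-daily dosing

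*Combined protocol and SAP*

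**What the plan says.** Section 3.4.4 sets the definition: "an overdose is defined as any daily dose that exceeds 2 times the prescribed dose in a 12-hour period". Section 1.6 gives caspofungin at 2 mg/kg once daily, and for the comparator, "Amphotericin B deoxycholate will be administered at 1 mg/kg once daily".

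Section 3.4.4.1 then separates two cases. Where an adverse experience results from the overdose, "the adverse experience(s) is reported as a serious adverse experience, even if no other criteria for serious are met". Where there are no associated clinical symptoms or abnormal laboratory results, "the overdose is reported as a non-serious Event of Clinical Interest (ECI").

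Table 3-5 in section 3.4.6 opens its seriousness row with "A serious adverse experience is any adverse experience occurring at any dose that", and one of the listed criteria reads "Is an overdose (Whether accidental or intentional.) Any overdose whether or not associated with an adverse experience must be reported within 24 hours". The causality part of the same table, under the category for no reasonable possibility of a drug relationship, adds "Also entered for a subject with overdose without an associated AE".

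Section 3.4.5.2, which sets out the events of clinical interest for the trial, gives only a combined hepatic laboratory criterion.

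**The concern.** A site that dispenses too much drug to an infant who shows no effect has two instructions. Section 3.4.4.1 makes the event non-serious. Table 3-5, the working reference for grading seriousness, names overdose as a criterion and makes no exception for this case. A site that looks for overdose in section 3.4.5.2, to confirm that it is an event of clinical interest, does not find it there.

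Serious adverse experience incidence is one of the six safety endpoints in section 3.5.4.2 and a Tier 2 comparison with a 95% confidence interval in Table 3-7. It is also one of the blinded counts that the Data Monitoring Committee receives under section 3.3.4. If coding depends on which page a site consults, that count mixes two conventions. Seriousness also carries a duty under section 3.4.5.1 to follow the patient for outcome.

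The definition has a second, smaller problem. It ties a daily dose to a 12-hour period for drugs given every 24 hours, so two careful readers can disagree on whether a given pattern of repeat dosing is an overdose.

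**Working it through.** **1. Classification, set side by side.**

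- *Adverse experience resulting from an overdose.* Section 3.4.4.1: serious. Table 3-5: serious. These agree.
- *Overdose without symptoms or abnormal laboratory results.* Section 3.4.4.1: non-serious event of clinical interest. Table 3-5: meets a seriousness criterion, no exception stated. Section 3.4.5.2: not listed. These conflict.
- *Reporting clock.* Sections 3.4.4 and 3.4.4.1 and Table 3-5 all require a report within 24 hours, with or without an adverse experience. These agree.
- *Causality.* Table 3-5 places an overdose without an adverse experience in the unrelated category, so the drug-related serious endpoint does not move.

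The conflict is therefore confined to the seriousness label of an overdose without effect.

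**2. Size per event.** The planned groups are about 60 and 30 (section 1.5). The endpoint is the percentage of patients with an event, so a recoded overdose changes it only if that infant has no other serious adverse experience. In that case:

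- caspofungin: 1/60 = 1.7 percentage points;
- amphotericin B deoxycholate: 1/30 = 3.3 percentage points.

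The documents give no overdose frequency. If, as an assumption, 0 to 2 such infants occur in an arm, the shift runs from 0 to 2/60 = 3.3 points on caspofungin, or from 0 to 2/30 = 6.7 points on the comparator.

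**3. The time window.** Inputs: one prescribed dose per day and infusion over about 2 hours (section 1.6); cut-off strictly above 2 times the prescribed dose (section 3.4.4).

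Take three full doses started at 0, 8 and 16 hours.

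- Over 24 hours: 3 × the prescribed daily dose. Since 3 > 2, this is an overdose if the daily dose governs.
- Over any 12 hours: to include part of all three infusions, a window must span from the end of the first (2 h) to the start of the third (16 h), which is 16 − 2 = 14 hours. Since 14 > 12, no 12-hour window reaches more than two doses. The maximum is 2.0 times, which does not exceed 2, so this is not an overdose if the 12-hour period governs.

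Table 3-4 refers to a 1-hour infusion. With that length the gap is 16 − 1 = 15 hours and the result is the same.

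**4. Exact doubling.** The cut-offs are 2 × 2 = 4 mg/kg for caspofungin and 2 × 1 = 2 mg/kg for amphotericin B deoxycholate, and a dose must be strictly above them. One duplicated infusion totals exactly 2.0 times and falls outside whether the window is 12 or 24 hours. This follows from the threshold, not from the window.

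**The case against.** The best defence is that Table 3-5 grades adverse experiences only. Section 3.4.3 defines these as unfavorable changes in the body's structure, function or chemistry, and an overdose without effect is not one. On that reading section 3.4.4.1 is the specific rule, the phrase in the table about overdoses with or without an adverse experience governs only the 24-hour clock, and the list in section 3.4.5.2 is open-ended. This is a plausible reading, and it may be what the sponsor intended. It does not remove the conflict. The table names overdose itself as a criterion and, in the same entry, speaks of overdoses that have no adverse experience, so a site can reasonably conclude that it applies to them. The causality note does not settle the matter, because it says nothing about seriousness.

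A reader might infer more than the documents support:

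- *That overdose in general is non-serious in section 3.4.4.1.* It is not; an adverse experience resulting from overdose is serious in both places.
- *That overdoses go unreported.* Every event meeting the definition reaches the sponsor within 24 hours under all three provisions. For doses below the cut-off, section 3.5.10 has incorrect doses described in the study report. Adverse experiences are still recorded, and serious ones are still reported within 24 hours.
- *That leaving out exact doubling is an error, given that the two regimens differ by a factor of 2.* The documents contain no standard by which a doubled dose must count, and they describe no preparation mix-up between arms. Section 2.4.2 does not say that one pharmacist prepares both drugs, and section 3.5.10 expects incorrect dosing to be uncommon. The threshold may be deliberate.

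**Conclusion.** The contradiction stands, in a narrow form. An overdose without symptoms or abnormal laboratory results can be coded serious or non-serious depending on the section consulted. The effect is on the serious adverse experience endpoint and the committee's serious-event counts, by at most 1.7 or 3.3 points per affected infant. This assumes the planned group sizes and no other serious event in that infant. No expected total can be given without an overdose frequency, and section 3.5.4.2 plans no formal safety testing, so no hypothesis test is at risk.

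The window in section 3.4.4 is a genuine ambiguity: the pattern of three doses at 8-hour intervals counts under one phrase and not under the other. Whether a dose of exactly twice the prescribed amount should count is a question for the clinical team, not a demonstrated fault.

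**What to change.** Reconcile section 3.4.4.1, section 3.4.5.2 and Table 3-5 so that one classification applies to an overdose without an adverse experience. If it remains an event of clinical interest, name it in section 3.4.5.2 and state the exception in the seriousness row of the table. If it is to be serious, change section 3.4.4.1 to match.

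Reconcile the time window in section 3.4.4 with the once-daily schedule, so that a single reading decides whether repeat doses count. Ask the clinical team to confirm whether leaving out exactly twice the prescribed dose is intended. No threshold, dose or clinical rule is proposed here.

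The cost is an amendment to reporting wording and brief site retraining. If any overdose without effect has already been reported, its coding should be checked against the agreed rule before unblinding.
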